Table 5	Criteria for Potentially Clinically Important Laboratory Values – Urinalysis.....	42
Table 6	Criteria for Potentially Clinically Important Vital Signs	44
Table 7	Criteria for Potentially Clinically Important ECG Values	45

LIST OF FIGURES

Figure 1	Schematic of Study Design.....	13
----------	--------------------------------	----

ABBREVIATIONS

AE	adverse event
ANOVA	analysis of variance
ANCOVA	analysis of covariance
ATC	Anatomical Therapeutic Chemical
AUC	area under the curve
BMI	body mass index
CMH	Cochran-Mantel Haenszel
COVID-19	Coronavirus disease 2019
C-SSRS	Columbia-Suicide Severity Rating Scale
ECG	electrocardiogram
eCRF	electronic case report form
EOT	end of treatment
ET	early termination
FAAM	Foot and Ankle Ability Measure
GESD	Global Evaluation of Study Drug
GSD	Guidance for Site Documentation and Data Management Querying of Data Impacted by COVID-19
ICE	intercurrent event
MAR	Missing at random
MCMC	Markov chain Monte Carlo
MedDRA	Medical Dictionary for Regulatory Activities
MI	Multiple imputation
MME	Morphine milligram equivalents
MNAR	Missing not at random
msec	milliseconds
NRS	numerical rating scale
PCI	potentially clinically important
ORAE	opioid-related adverse event
QTcB	QT interval corrected for heart rate using Bazett's formula
QTcF	QT interval corrected for heart rate using Fridericia's formula
SAE	serious adverse event
SAP	statistical analysis plan
SD	standard deviation
SE	standard error
SOC	system organ class

TEAE treatment-emergent adverse event
TESAE treatment-emergent serious adverse event

1 INTRODUCTION

This statistical analysis plan (SAP) provides a technical and detailed elaboration of the statistical analyses of safety and efficacy data as described in the study protocol Version 1.0 amendment 5 dated 01 February 2022.

Specifications for tables, figures, and listings are contained in a separate document. Statistical analyses for population pharmacokinetic (PK) and PK/pharmacodynamics (PD) modeling will be presented in a separate report and therefore will not be included in this SAP.

This plan should be read in conjunction with the study protocol and the electronic case report forms (eCRF).

2 OBJECTIVES

2.1 Primary Objective

The primary objective of this study is to evaluate the efficacy of ACP-044 compared with placebo in the treatment of acute postoperative pain.

2.2 Secondary Objectives

The secondary objectives of this study are to evaluate the efficacy of ACP-044 compared with placebo in the treatment of acute postoperative pain and to evaluate opioid use among ACP-044 treated subjects compared with placebo in the treatment of acute postoperative pain.

2.3 Exploratory Objectives

The exploratory objectives of this study are to evaluate the proportion of subjects with severe pain and to compare the impact of ACP-044 on activities of daily living compared with placebo in the treatment of acute postoperative pain.

2.4 Safety Objective

The safety objective of this study is to evaluate the safety and tolerability of ACP-044 compared with placebo in the treatment of acute postoperative pain.

2.5 Pharmacokinetic Objective

The pharmacokinetic objective of this study is to characterize the pharmacokinetic (PK) profile of ACP-044 in subjects treated for acute postoperative pain.

2.6 Pharmacokinetic/Pharmacodynamic Objective

The pharmacokinetic/pharmacodynamic objective of this study is to characterize the exposure-response relationship using appropriate modelling and simulation methods.

3 STUDY DESIGN

3.1 General Study Design

This study will be conducted as a Phase 2, randomized, double-blind, placebo-controlled, multicenter study in subjects with acute postoperative pain (following bunionectomy surgery). The study will compare each of the two active treatment groups receiving a total daily dose of 1600 mg ACP-044, administered either once daily or 400 mg every 6 hours, with a placebo group. The Sponsor, subjects, and Investigators will be blinded to treatment assignment.

Approximately three sites in the United States (US) will screen approximately 375 subjects and approximately 240 subjects are planned for enrollment (80 subjects per treatment group).

The duration of participation for individual study subjects will be approximately 9 weeks, consisting of a screening period of up to 4 weeks, a 4-day treatment period, and a safety follow-up period of approximately 30 (+4) days.

The study periods are:

- Screening: up to 4 weeks (prior to surgery)
- Double-blind treatment: Day -1 (post first dose of study drug/day of surgery) to Day 4
- Safety follow-up: approximately 7 days after end of treatment (EOT)/early termination (ET) and approximately 30 days (post last dose of study drug)

The study start date is defined as the date the first subject signs the informed consent form.

The study completion date is defined as the date the final subject, across all sites, completes their final protocol-defined assessment. Please note: this includes the safety follow-up visit or contact.

Screening Period

During the Screening period, subjects will be assessed for study eligibility. Only those subjects who meet all inclusion and no exclusion criteria will be eligible for the study.

All prohibited medications should be discontinued during the Screening period and prior to surgery. Investigators must not withdraw a subject's prohibited medication for the purpose of enrolling them into the study. Medications will be discontinued only if it is deemed clinically appropriate to do so and in consultation with the prescribing physician.

With approval of the Medical Monitor, rescreening of a subject will be allowed one time if there is an extenuating circumstance that was not under the subject's control or if is due to an

identifiable cause, and it is medically appropriate to address that cause, and there is no medical reason that would prevent the subject to be rescreened and enrolled in the study.

Treatment Period

The first dose of study drug will be administered within 60 (± 15) minutes prior to the start of surgery. Subjects will then have a popliteal and/or ankle nerve block administered to anesthetize the knee, distal leg, and foot, after which they will enter into surgery. Following surgery, subjects will be administered the remaining three daily doses approximately every 6 hours after the initial dose.

Day 1 is defined as the day after surgery. The popliteal and/or ankle nerve block will be discontinued approximately 2-4 hours prior to the first dose on Day 1 (i.e., the fifth dose of the study) and nerve block removal; a discontinuation window of approximately 2 hours is permitted. The time at which the first dose on Day 1 is administered will be time 0 for all pain assessments. Study drug administration and study procedures are to be completed on Days -1 through 4 according to the schedule of assessments ([Section 21.1](#)). Subjects will be encouraged to refrain from taking rescue medication until 1-2 hours following the first dose of study drug on Day 1.

[figure not shown]
On Day 4, after the 72 hour pain assessments are performed, the EOT procedures will be completed and subjects will be discharged from the clinical site.

Safety Follow-up Period

Safety will be further assessed during a follow-up visit to occur in the clinic approximately 7 (± 3) days after EOT/ET procedures and subjects will receive a follow-up telephone call approximately 30 (+4) days after the last dose of study drug. Subjects should return to standard of care after the follow-up visit that will occur in the clinic 7 (± 3) days after the EOT/ET.

The study schematic is presented in [Figure 1](#).

Figure 1 Schematic of Study Design

Abbreviations: EOT=end of treatment

^a Subjects to be randomized in a 1:1:1 ratio to receive either a once-daily oral dose of 1600 mg ACP-044, four oral doses of 400 mg ACP-044, or placebo. Randomization will occur just prior to surgery when the first dose of study drug is given.

^b The time at which the first dose on Day 1 (i.e., the fifth dose of study drug) is administered will be considered time 0 for pain assessments.

3.2 Schedule of Assessments

Schedule of events and assessments can be found in [Section 21.1](#).

3.3 Randomization

On Day -1 eligible subjects who meet inclusion and do not meet exclusion criteria will be randomized in a 1:1:1 ratio to receive 1600 mg ACP-044, administered either once daily or 400 mg every 6 hours, or placebo, according to a randomization schedule. Randomization will be stratified by site.

Approximately three sites in the United States (US) will screen approximately 375 subjects and approximately 240 subjects are planned for randomization (80 subjects per treatment group).

3.4 Blinding

Treatment assignments will be blinded to all study subjects, Investigators, site personnel (with the exception of the unblinded pharmacist and verifier), and Sponsor personnel. An unblinded pharmacist and a verifier will prepare the study drug and shall have no role in pain assessment or patient care.

In order to maintain the double-blind design of the study, all subjects will receive the same numbers of tablets at the same intervals (four times per day), regardless of the treatment group to which they are randomized. Placebo tablets will be size- and color-matched to the ACP-044 tablets.

Table 1 Blinded Daily Dosing Regimen

	First Daily Dose	Second Daily Dose	Third Daily Dose	Fourth Daily Dose
Placebo	PPPP	P	P	P
ACP-044 400 mg (every 6 hours)	XPPP	X	X	X
ACP-044 1600 mg (once-daily)	XXXX	P	P	P

Abbreviations: P=ACP-044 placebo tablet; X=ACP-044, 400 mg tablet

3.5 Determination of Sample Size

The planned sample size is 240 randomized subjects (80 subjects per treatment group).

Assuming a treatment difference in the AUC from 0 to 24 hours is 23 points between the ACP-044 groups and placebo group, and the common standard deviation is 50 points, 76 subjects per treatment arm will provide approximately 80% power to detect the assumed treatment difference using a t-test between each ACP-044 dose arm and placebo at a 2-sided significance level of 0.05. Assuming no more than 5% of randomized subjects will be excluded from primary efficacy analysis, 80 subjects per treatment group will be randomized.

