- 17. Has received an investigational product or device in a clinical trial within 30 days or within five elimination half-lives, whichever is longer, prior to Screening
- 18. Is an employee or is a family member of an employee of Acadia Pharmaceuticals Inc. or the clinical research site or the clinical research organization (CRO) administering this study
- 19. Is judged by the Investigator or the Medical Monitor to be inappropriate for the study

Pharmacokinetic assessments

At each predefined timepoint, a total of six (6) PK samples will be obtained for measurement of concentrations of ACP-044. PK blood samples will be collected Day -1 (predose, within one hour of dosing), Day 1 (one sample taken between 2-3 hours and one sample taken between 4-6 hours, after the first dose of the day), Day 2 (prior to the first dose of the day), and Day 3 (one sample taken between 2-6 hours and one sample taken between 8-12 hours, after the first dose of the day).

When possible, an additional PK sample will be collected from subjects who experience a serious adverse event (SAE) or an adverse event (AE) leading to discontinuation, as soon as possible after the occurrence of that event. For samples collected from subjects who experience an SAE or an AE leading to discontinuation, the date and time of the last dose prior to the SAE or AE should also be recorded.

ACP-044 plasma concentration data will remain blinded until the unblinding of the clinical database at the end of the study.

Sample size calculations

The planned sample size is 240 subjects randomized (80 subjects per treatment group). Randomization will be stratified by site.

Assuming a treatment difference in the AUC from 0 to 24 hours is 23 points between the ACP-044 groups and placebo group, and the common standard deviation is 50 points, 76 subjects per treatment arm will provide approximately 80% power to detect the assumed treatment difference between each ACP-044 dose arm and placebo at a 2-sided significance level of 0.05. Assuming no more than 5% of randomized patients will be excluded from primary efficacy analysis, 80 subjects per treatment group will be randomized.

Statistical methods

Population Analysis Sets

The **Safety Analysis Set** includes all randomized subjects who received at least one dose of study drug (ACP-044 or placebo). Subjects will be analyzed based on the treatment that they actually received. The Safety Analysis Set will be used for all safety analyses.

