9.2.1 Multiple Comparisons/Multiplicity

A fixed-sequence method at alpha=0.05 for the primary and key secondary efficacy endpoints will be used to control for multiplicity. The following will be the sequence for testing:

- 1. 400 mg Q6H compared to placebo on mean AUC₀₋₂₄ of NRS of pain intensity scores
- 2. 1600 mg QD compared to placebo on mean AUC₀₋₂₄ of NRS of pain intensity scores
- 3. 400 mg Q6H compared to placebo on time to first rescue medication use after time 0
- 4. 400 mg Q6H compared to placebo on proportion of subjects who were opioid free through 24 hours
- 5. 1600 mg QD compared to placebo on time to first rescue medication use after time 0

Study: ACP-044-004 Clinical Study Protocol Amendment 5

6. 1600 mg QD compared to placebo on proportion of subjects who were opioid free through 24 hours

- 7. 400 mg Q6H compared to placebo on proportion of subjects who were opioid free through 48 hours
- 8. 1600 mg QD compared to placebo on proportion of subjects who were opioid free through 48 hours
- 9. 400 mg Q6H compared to placebo on proportion of subjects who were opioid free through 72 hours
- 10. 1600 mg QD compared to placebo on proportion of subjects who were opioid free through 72 hours

The testing procedure will stop once a p-value in the sequence is greater than 0.05. P-values that are less than or equal to 0.05 prior to stopping, will be declared statistically significant; p-values after stopping will be nominal.

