9.5.2 Primary Analyses

The primary efficacy variable, AUC₀₋₂₄, will be analyzed by using analysis of variance (ANOVA) with treatment group and site as factors in the model. Each active dose group will be compared to placebo using this model. P-value and associated 95% confidence interval for treatment difference between each active dose and placebo will be presented. Missing pain assessment at scheduled time point will be imputed. The details of missing data imputation and multiplicity adjustment will be described in the SAP.

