12.3 Multiple Comparisons / Multiplicity

A fixed sequence method at alpha=0.05 for the primary and key secondary efficacy endpoints will be used to control for multiplicity. The following will be the sequence for testing:

1. 400 mg Q6H compared to placebo on mean AUC_{0-24} of NRS of pain intensity scores
2. 1600 mg QD compared to placebo on mean AUC_{0-24} of NRS of pain intensity scores
3. 400 mg Q6H compared to placebo on time to first rescue medication use after time 0
4. 400 mg Q6H compared to placebo on proportion of subjects who were opioid free through 24 hours
5. 1600 mg QD compared to placebo on time to first rescue medication use after time 0
6. 1600 mg QD compared to placebo on proportion of subjects who were opioid free through 24 hours
7. 400 mg Q6H compared to placebo on proportion of subjects who were opioid free through 48 hours

8. 1600 mg QD compared to placebo on proportion of subjects who were opioid free through 48 hours
9. 400 mg Q6H compared to placebo on proportion of subjects who were opioid free through 72 hours
10. 1600 mg QD compared to placebo on proportion of subjects who were opioid free through 72 hours

The testing procedure will stop once a p-value in the sequence is greater than 0.05. P-values that are less than or equal to 0.05 prior to stopping, will be declared statistically significant; p-values after stopping will be nominal. P-values obtained from the stratified log-rank test stratified by site will be used to for the endpoints that compare the time to first rescue medication use after time 0 by treatment group.

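### The stated 80% power for each ACP-044 arm is that of one ungated t-test; under the plan's fixed sequence 1600 mg QD has about 70%

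*SAP*

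**What the plan says.** The sample-size text appears in three places. For the comparisons with placebo, SAP 3.5 states that "76 subjects per treatment arm will provide approximately 80% power to detect the assumed treatment difference using a t-test between each ACP-044 dose arm". The test is two-sided at 0.05. Protocol 9.3 and the synopsis carry the same claim without naming the test: "76 subjects per treatment arm will provide approximately 80% power to detect the assumed treatment difference between each ACP-044 dose arm and placebo". The inputs are a 23-point difference in AUC0-24, applied to both ACP-044 groups, and a common SD of 50. To allow for up to 5% excluded from the primary analysis, 80 per arm are randomized.

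The decision rule is set out elsewhere. Protocol 9.2.1 says: "A fixed-sequence method at alpha=0.05 for the primary and key secondary efficacy endpoints will be used to control for multiplicity". Step 1 is 400 mg Q6H versus placebo on AUC0-24, step 2 is 1600 mg QD versus placebo on AUC0-24, and steps 3 to 10 are the key secondary comparisons. SAP 12.3 repeats the list and the stopping rule: "The testing procedure will stop once a p-value in the sequence is greater than 0.05". Results at or below 0.05 before that point "will be declared statistically significant; p-values after stopping will be nominal".

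None of the three sample-size passages mentions the sequence, and neither document gives a power figure that takes it into account.

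**The concern.** The power statement covers each active arm, but the two arms do not face the same test. Q6H needs only its own p-value at or below 0.05. QD needs that as well, and it also needs Q6H to have succeeded first. A significance claim for QD is therefore the event that both tests succeed, and this is less likely than either success alone. A reader of the sample-size section would reasonably take 80% as the chance of a significant result for either regimen.

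The same event opens steps 3 to 10. The chance that any key secondary endpoint is formally tested, including those for Q6H, is the probability that both primary tests succeed, and the documents do not give it.

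Protocol 1.5.2 says it is unclear whether response is driven by peak concentration or by AUC, and that two regimens are tested to help choose between them. The plan thus allows that they may differ, so the dependence of QD on the Q6H result matters.

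**Working it through.** **Inputs, all from the plan.** Difference δ = 23 in both arms and SD σ = 50 (SAP 3.5, Protocol 9.3); two-sided α = 0.05; n = 76 evaluable per arm, 80 randomized; 1:1:1 allocation with one placebo group (SAP 3.3); Q6H at step 1 and QD at step 2 (SAP 12.3, Protocol 9.2.1).

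**1. Reproduce the stated figure.** The noncentrality of one comparison is δ / (σ√(2/n)).

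- n = 76: 23 / (50 × √(2/76)) = 2.836
- n = 80: 23 / (50 × √(2/80)) = 2.909

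Power of a single two-sided test:

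| Method | n = 76 | n = 80 |
|---|---|---|
| Normal approximation | 80.9% | 82.9% |
| t-test, df = 2n − 2 | 80.4% | 82.4% |
| Three-arm ANOVA, df = 3n − 5 (3 treatments, approximately 3 sites) | 80.6% | 82.6% |

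The 80% reproduces as one ungated comparison. The dropout allowance also reproduces: 76 / 0.95 = 80.

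**2. Power for QD under the sequence.** QD can be declared significant only if both p-values are at or below 0.05. The two test statistics share the placebo mean, so with equal arms their correlation is 0.5.

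- Bivariate normal approximation at n = 76: each margin is 2.836 − 1.960 = 0.876, and Φ₂(0.876, 0.876; ρ = 0.5) = 70.0%.
- With the pooled variance and df = 3n − 5, integrating over the shared placebo mean and the pooled SD: **69.6% at n = 76 and 72.3% at n = 80**.
- Simulation with 1,000,000 replicates: 69.6% and 72.2%.
- Simulation with separate two-sample t-tests (400,000 replicates): 69.3% and 72.2%.

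Treating the tests as independent would give 65.5% at n = 76, which is wrong here because the placebo group is shared.

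**3. Size of the gap.** At n = 76, 80.6% − 69.6% = 11.0 points. This is the share of trials in which QD has p≤0.05 and Q6H does not. Simulation gives 11.0% at 76 and 10.3% at 80.

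**4. Dependence on the Q6H effect.** The following Q6H effects are assumptions made here and are not in the documents. QD is held at 23 with n = 76.

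| True Q6H effect | Probability QD is formally significant |
|---|---|
| 23 (the plan) | 69.6% |
| 20 | 61.1% |
| 11.5 | 27.7% |
| 0 | 3.4% |

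The 70% figure does not depend on the last three rows.

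**The case against.** The strongest reply is that no stated number is wrong. SAP 3.5 describes a t-test of each arm against placebo, and as a per-comparison power 80% is correct for both arms. Quoting per-comparison power and setting out the multiplicity rule separately is a reporting choice. The sequence is fully disclosed, and Protocol 9.2.1 comes directly before 9.3. This is a proof-of-concept Phase 2 trial, and QD is reported whatever happens at step 1, since Protocol 9.5.2 promises that "P-value and associated 95% confidence interval for treatment difference between each active dose and placebo will be presented". In addition, 76 is the low end: if nobody is excluded, the QD figure is 72.3%.

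Much of this stands. The arithmetic of the single comparison is sound. Only the formal claim of significance for QD is affected, not what is estimated or reported. The scenarios with a smaller Q6H effect show how a fixed sequence behaves and carry no weight for the size of the problem under the plan's assumptions.

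It does not remove the point. Naming a t-test does not say that the figure ignores the gate, and the protocol text does not even name the test. The plan chose formal control over ten tests, so the power of that decision rule is what the sample-size section should report. The gap is still about 10 points with all 80 evaluable.

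**Conclusion.** The concern holds. The 80% describes one ungated comparison and, under the plan's decision rule, applies only to 400 mg Q6H. For 1600 mg QD, and for access to any key secondary test, the figure is about 70% at 76 evaluable per arm and about 72% at 80. This rests on the plan's own inputs: a true difference of 23 in both arms, SD 50, equal allocation and a shared placebo group. Adding site to the model makes a negligible difference. The sequence does not inflate type I error; the defect is confined to the power statement, which should be corrected.

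**What to change.** In SAP 3.5, Protocol 9.3 and the synopsis, restate the power along these lines:

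> With 76 evaluable subjects per arm, power is about 80% for 400 mg Q6H. Under the fixed sequence it is about 70% for 1600 mg QD, and for success on both regimens (about 72% if all 80 per arm are evaluable).

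The 80% per-comparison figure for QD may stay beside it if labelled as the power of the ungated test. It would also help to say that the 70% is the chance of reaching step 3.

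The cost is one sentence in three places, with no change to the sequence, tests, alpha or sample size. The two protocol places count as a protocol modification and go to the IRB/EC as an amendment or notification (Protocol 10.7); the SAP sentence can be added on its own first. The plan would then show a less favourable figure for QD and for the key secondary tests. For scale only, 80% for QD under the sequence would need about 93 evaluable per arm by the normal approximation, or 93 / 0.95 ≈ 98 randomized; that is not proposed.
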